6.2.3. Sensitivity, Covariate and Subgroup Analyses

The ASNase concentration on Day 14 following the first and fourth infusion for each patient will be linearly dose adjusted from 150 U/kg to 100 U/kg and the proportion of patients with values >100 U/L determined.

The primary endpoint and key secondary endpoint will be evaluated in the subgroups listed below with data presented in Forest Plots (point estimates and 95% confidence intervals) for each endpoint together with the effect in the overall evaluable patients' population. The purpose of this evaluation is to assess the homogeneity of treatment effect.

Sponsor:	NOPHO – Nordic Society of Pediatric Hematology & Oncology		
Protocol:	NOR-GRASPALL 2016		
Document Version No.:	2.0	Document Date:	14-May-2021

Subgroups to be used:

- Gender
- Age (<18 years, \geq 18 years)
- for age <18: <11 years, 11- <18
- Antibody status at baseline (neutralizing activity as positive vs negative)
- Grade of allergic reactions to Oncaspar (Grade 1 and 2 combined vs Grade 3 and Grade 4 combined)
- Silent inactivation to Oncaspar (Yes, No)

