Safety analysis of the overall study period revealed a significantly lower overall incidence of drug-related AEs and SAEs in the eryaspase arm (73.1%, and 15.4%, respectively) compared to the control arm (100% and 35.7%, respectively). Similarly, the incidence of drug-related Grade 3 or 4 AEs was lower with eryaspase (57.7%) than native E.Coli asparaginase (89.3%).

The key adverse events of interest are generally considered to be class-effects relevant to L-asparaginase, including hypersensitivity reactions, coagulopathic events, pancreatic events and hepatic events. The majority of these events occurred at a lower frequency with eryaspase compared to native *E.Coli* asparaginase during overall study period (Table 1).

TABLE 1: SUMMARY OF KEY ADVERSE EVENTS OF INTEREST THAT ARE DRUG-RELATED AEs IN $\geq 10\%$ OF PATIENTS ARRANGED BY MEDDRA PREFERRED TERM

Preferred Term	ERYASPASE N=26 (%)	Control native asparaginase N= 28 (%)
At least one AE	19 (73.1)	28 (100)
Hypofibrinogenemia	7 (26.9)	18 (64.3)
Elevated amylase and/or lipase enzyme elevation	7 (26.9)	15 (53.6)
Transaminase increased	5 (19.2)	6 (21.4)
Hypoalbuminemia	4 (15.4)	9 (32.1)
Anti-thrombin III decreased	3 (11.5)	20 (71.4)
Hyperbilirubinemia	2 (7.7)	5 (17.9)
Drug hypersensitivity reactions	2 (7.7)	16 (57.1)
Hepatotoxicity	1 (3.8)	5 (17.9)
GGT increased	1 (3.8)	4 (14.3)
Activated partial thromboplastin time prolonged	1 (3.8)	3 (10.7)

Extras of Table 14.3.1.10.1 from clinical study report of the GRASPALL 2009-06 trial

Altogether, eryaspase was shown to demonstrate improved clinical efficacy and a better overall safety profile compared to native *E.Coli*-asparaginase in patients with relapsed or refractory ALL (22). Noteworthy, history of hypersensitivity reactions due to prior exposure to native or pegylated *E.Coli* asparaginase and anti-L-asparaginase antibodies status does not adversely impact the pharmacological activity and the safety profile of eryaspase in this patient population. Focusing on the key adverse events of interest, it has to be noted that only (3) 12% of patients who had previous allergic reactions to asparaginase experienced drug-related hypersensitivity reactions. The encouraging results with eryaspase in this pivotal trial provides a potential alternative treatment for these patients who might be at risk of hypersensitivity reactions and/or other asparaginase-related toxicities.

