The duration of treatment with eryaspase will be dictated by the remaining number of intended courses following the occurrence of hypersensitivity to PEG-asparaginase, and therefore ranges between 1-7 doses of eryaspase.

An interim analysis will be performed when 5 patients have been included.

It is estimated to include 45 children and 5 adults in this study. Patient enrolment will start in Denmark in January 2017. It is estimated that 50 patients will be enrolled by end of February 2020.

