4. GENERAL STATISTICAL CONSIDERATIONS AND DATA HANDLING

4.1. Sample Size Justification

The trial is powered to test the hypothesis that 70% of patients meet the >100 U/L threshold compared to the null hypothesis that this threshold is achieved in 50% of patients. The null and alternative hypotheses stated here align with those outlined in previous FDA approvals, such as CDER Application (125359Orig1s000) for Erwinaze in the treatment of ALL. Based on a one-sided significance level of 2.5%, a total of 49 patients will provide 80% power for this comparison in an exact binomial test. A total of 55 patients will be recruited to allow for a ~10% dropout rate for an analysis based on evaluable patients.

Originally, the study was planned for 30 patients. An interim analysis was conducted after first 18 patients enrolled into the study, and study continued to enroll all 35 patients. The protocol was amended in August 2019 to increase the sample size up to 55 patients. The sample size increase was prompted by:

1. Continuous Erwinaze shortage and the need to complete the intended courses of asparaginase therapy
2. Encouraging safety and efficacy profile based on the informal interim analysis in the first 18 patients
3. Note that the sample size increase was not based on any evaluation of the primary endpoint from the study data collected up to that point

The primary population for analysis will be the Evaluable Patient population defined as all patients recruited into the study who provide data on whole blood ASNase activity on Day 14 (+/- 2 days) following the first administration of eryaspase.

A formal statistical hypothesis test will be performed on the primary endpoint. A single sample binomial test will be used to test the null hypothesis at the 2.5% one-sided significance level. The key secondary endpoint with the threshold of 100 U/L following the fourth infusion will be evaluated in the same way. Multiplicity will be controlled across the primary and key secondary endpoint through a pre-specified hierarchy with the primary endpoint in position 1 and the key secondary endpoint in position 2.

Descriptive statistics will be presented. For binary endpoints, 95% confidence intervals for the observed proportions will be calculated using Wilson Score method.

Sponsor:	NOPHO – Nordic Society of Pediatric Hematology & Oncology		
Protocol:	NOR-GRASPALL 2016		
Document Version No.:	2.0	Document Date:	14-May-2021

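### SAP 6.2.3 sets out to assess homogeneity across subgroups but plans no between-subgroup difference or interval, so its forest plots cannot support a homogeneity conclusion in either direction

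*SAP*

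**What the plan says.** SAP 6.2.3 evaluates the primary endpoint (Day 14 after the first infusion) and the key secondary endpoint (Day 14 after the fourth infusion) in six subgroup pairs: gender, adult vs child, two age bands within children, baseline neutralizing antibody, grade of allergic reaction to Oncaspar, and silent inactivation to Oncaspar. The antibody factor is listed as "Antibody status at baseline (neutralizing activity as positive vs negative". The output is a forest plot of point estimates and 95% CIs for each endpoint, with the overall evaluable result. The stated aim is: "The purpose of this evaluation is to assess the homogeneity of treatment effect".

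No difference between subgroups, interval for a difference, interaction test, margin or reading rule is given. SAP 4.7 plans no covariate-adjusted analysis, 4.8 says multiplicity is not a concern, and 4.9 marks subpopulations as not applicable. SAP 4.1 and 6.1 name the Wilson score method for intervals on binary endpoints.

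The only subgroup sizes in the documents are for age. Protocol 5.1 says: "It is estimated to include 45 children and 5 adults in this study".

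**The concern.** Homogeneity is a statement about differences between subgroups. A plot of separate percentages leaves readers to compare intervals by eye, and whether two separate 95% intervals overlap is a poor guide to whether the difference is compatible with zero.

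The question matters in this trial. Every patient enters because of allergy to PEG-asparaginase or loss of its activity, so whether neutralizing antibodies or silent inactivation lower Day-14 activity is a central scientific question. This plot is the only analysis in the current SAP that sets antibody status against activity; SAP 6.4 describes antibody frequencies and seroconversion alone. Protocol 1.2 already reports from an earlier trial that "anti-L-asparaginase antibodies status does not adversely impact the pharmacological activity and the safety profile of eryaspase in this patient population". A plot of wide, overlapping intervals could be cited in support of that statement without adding real evidence for it.

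**Working it through.** **Inputs**
- Rates from SAP 4.1: the trial is powered for "70% of patients meet the >100 U/L threshold compared to the null hypothesis that this threshold is achieved in 50% of patients". The 50% vs 70% contrast below uses these two rates; 50% vs 80% and others are assumed for range.
- Size from SAP 4.1: "a total of 49 patients will provide 80% power for this comparison in an exact binomial test", and "A total of 55 patients will be recruited to allow for a ~10% dropout rate".
- Interval method: 95% Wilson, from SAP 4.1 and 6.1, assumed to carry over to 6.2.3.
- Splits of 49: 5/44 takes the protocol's estimate of 5 adults. 15/34 and 25/24 are assumptions, because the documents give no sizes for the antibody, allergy-grade, silent-inactivation or gender subgroups.

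**Step 1. The plan's own figure.** For X ~ Binomial(49, p), the smallest cut-off with exact one-sided alpha at most 0.025 is 32. P(X ≥ 32 | 0.5) = 0.0222 and P(X ≥ 32 | 0.7) = 0.810. Dropout: 49/(1 − 0.10) = 54.4, rounded up to 55. Both figures reproduce.

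**Step 2. Formulas for the subgroup comparison** (z = 1.96)
- Wilson limits (l, u) = [p̂ + z²/(2n) ± z√(p̂(1−p̂)/n + z²/(4n²))] / (1 + z²/n).
- Newcombe-Wilson limits for d = p̂₁ − p̂₂: lower = d − √[(p̂₁−l₁)² + (u₂−p̂₂)²]; upper = d + √[(u₁−p̂₁)² + (p̂₂−l₂)²].
- Detection probability = the sum, over all outcomes (x₁, x₂), of the product of the two binomial probabilities whenever the two Wilson intervals do not overlap (rule A) or the difference interval excludes 0 (rule B).

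**Step 3. Detection by exact enumeration** (lower rate in the first-named group)

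| True rates | Rule | 5/44 | 15/34 | 25/24 |
|---|---|---|---|---|
| 50% vs 70% | A: non-overlap | 6.0% | 7.7% | 8.8% |
| 50% vs 70% | B: difference CI | 18.8% | 28.6% | 29.0% |
| 50% vs 80% | A | 16.2% | 24.8% | 29.1% |
| 50% vs 80% | B | 39.3% | 56.9% | 61.0% |
| 50% vs 90% | A | 36.1% | 61.5% | 66.3% |
| 50% vs 90% | B | 66.9% | 86.5% | 90.1% |
| 70% vs 70% | A | 0.8% | 0.5% | 0.5% |
| 70% vs 70% | B | 4.1% | 4.8% | 5.1% |

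Under rule A the miss rate is therefore 91-94% at 50% vs 70% and 71-84% at 50% vs 80%. Under rule B it is 71-81% and 39-61%.

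**Step 4. Dependence on the base rate.** For other 20-point differences, rule A misses about 90-92% at 60% vs 80% and 83-89% at 70% vs 90% over the same splits. If all 55 recruits were evaluable and evenly split, the miss at 50% vs 70% would be about 89%.

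**Step 5. An example.** Take 15/25 (60.0%; Wilson 40.7 to 76.6%) and 21/24 (87.5%; 69.0 to 95.7%). The intervals overlap. The difference is −0.275; lower = −0.275 − √(0.1926² + 0.0816²) = −0.484; upper = −0.275 + √(0.1660² + 0.1850²) = −0.026. The interval for the difference excludes 0 although the two plotted intervals overlap.

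**Step 6. Precision in general.** By the simple normal approximation at 50% vs 70%, the half-width of a 95% interval for the difference is 1.96√(0.25/25 + 0.21/24) = 0.27 at 25/24 and 1.96√(0.25/5 + 0.21/44) = 0.46 at 5/44. A difference of 20 points or more usually remains compatible with the data whichever display is used.

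**The case against.** The strongest reply is that SAP 6.2.3 never says overlap is the criterion. That is correct. The plot also shows point estimates and the overall value, so the overlap figures describe one way of reading it. Nor would the plots almost always look homogeneous: at a true 50% vs 70% the two point estimates differ by at least 15 points in 63-65% of trials over the three splits. But the same enumeration gives a gap that large in 26-50% of trials when both rates are 70%, so the point estimates alone do not settle the matter.

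Second, a reader might infer that the trial will report equal activity in all subgroups whenever no difference is visible. No text says so; that is a possible use of the plot and not a planned conclusion. The antibody statement in Protocol 1.2 concerns an earlier trial and does not show how this SAP will be interpreted. A reader might also take that statement to rest on the 26 eryaspase patients in Protocol Table 1 alone, but Protocol 2.1.2 refers to both eryaspase arms, allergic and non-allergic.

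Third, small subgroups are the main cause. The difference interval improves detection but still misses most 50% vs 70% differences. This stands, and it limits what the remedy can claim.

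Fourth, six pairs and two endpoints give up to 12 intervals, so some chance findings are likely. This also stands and needs a label.

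SAP 4.7 is no obstacle: it excludes covariate-adjusted analysis, not an unadjusted difference.

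**Conclusion.** The point holds as a gap between purpose and output. SAP 6.2.3 names homogeneity as its aim and never produces the comparison that bears on it. Under an overlap reading, which the SAP does not state, a 50% vs 70% difference would be missed about 91-94% of the time and 50% vs 80% about 71-84%. A direct interval would cut these to 71-81% and 39-61%, with false positives near 5%.

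These figures assume 49 evaluable patients, Wilson intervals, the lower rate in the first-named group, and splits that are assumed except for age. Even the age split takes an estimate made for 50 enrolled patients and applies it to 49 evaluable. It would be too strong to say that any 20-point difference is missed more than 90% of the time, since the miss falls to 83-89% at 70% vs 90%. For the key secondary endpoint the subgroups can be no larger, because patients may receive as few as one dose, so precision is no better.

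The trial cannot establish homogeneity either way. The primary test is untouched; what is at risk is an unsupported secondary statement, above all on neutralizing antibodies.

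**What to change.** In SAP 6.2.3, for each of the six subgroup pairs and for both endpoints, add the difference in the percentage above 100 U/L with a Newcombe-Wilson 95% CI, and show it on the forest plots. Label the intervals descriptive and unadjusted for multiplicity (6 × 2 = up to 12).

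Replace the purpose sentence with: *to describe differences between subgroups; homogeneity will not be concluded from overlapping intervals or from a difference CI that includes 0.*

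The cost is one sentence and one more column in two planned figures, with no new data. The intervals will be wide, especially for adults, and some of the 12 comparisons may exclude zero by chance.

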6.3. Analysis of Secondary Pharmacodynamic Endpoints

6.3.1. Cerebrospinal Fluid Pharmacodynamics

Cerebrospinal fluid samples for ASN, GLN, ASP, and GLU will be drawn when intrathecal therapy occurs. The amino acid concentrations will be provided as follows:

- Summary statistics at various time points and presented by subject and actual sample collection time relative to eryaspase administration.
- Individual patient profile plots of amino acid levels will be presented at each time point.

6.3.2. Other Pharmacodynamic Endpoints

Levels of cytotoxic methotrexate (MTX polyglutamates) and 6-mercaptopurine metabolites (6-thioguanine nucleotides, 6TGN, and methylated metabolites, MeMP) and of DNATGN levels in circulating leukocytes will be summarized over time using descriptive statistics.

Additional exploratory analyses include:

- Correlating serum albumin levels at D14 with Cmax and AUC at steady state.

These two endpoints will be presented in a scatterplot with ASNase activity at Day 14, and Pearson's correlation coefficient will be calculated for each endpoint.

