essential that all asparaginase-doses must be substituted with Erwinase in the future NOPHO-protocols in case of allergy or "silent inactivation" unless a better alternative is found. This induce a huge number of hospitals visit for the patients.

According to the NOPHO ALL 2008 protocol, maintenance treatment phases include thiopurines e.g. 6-mercaptopurine (6-MP) and methotrexate (MTX). 6-MP is a prodrug and its cytotoxicity depends on conversion to 6-thioguanine nucleotides (TGN). TGN are incorporated into DNA (DNA-TGN) and are occasionally mismatched to thymidine, causing cell death by post-replicative mismatch repair (11).

It has been suggested that asparaginase may reduce the metabolism and thus increase the toxicity of other drugs. Furthermore, asparaginase-associated hypoproteinemia, which leads to higher free drug levels of other chemotherapeutics, has also been proposed as a contributing factor of in this context (12).

Analysis of data (publication under preparation) from the NOPHO-protocol indicates increments of 6MP and MTX metabolites levels during the treatment of PEG-asparaginase. This emphasize that asparaginase can have a major impact on 6MP and MTX metabolism and thus their toxic effect. Accordingly, PEG- asparaginase has been previously associated with increased myelotoxicity and higher frequency of 6MP/MTX dose reductions during maintenance therapy for childhood ALL (13). Furthermore, it is shown that the higher levels of 6MP metabolite levels were associated with an increased risk of hepatic sinusoidal obstruction syndrome (SOS). Data from NOPHO ALL 2008 indicates that the hepatotoxicity is increased when 6MP is given in combination with continuous PEG-asparaginase (14). Further studies are planned and in progress, but it is important to investigate in studies with alternative formulations of asparaginase.

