3.2 Secondary Objectives

- To assess the immunogenicity of eryaspase as determined by assessment of anti-L-asparaginase antibodies and neutralizing antibodies.
- To assess the overall safety and tolerability of eryaspase in combination with multi-agent NOPHO ALL 2008 chemotherapy according to the PdL toxicity consensus definitions for asparaginase related toxicities (hypersensitivity, pancreatitis, hyperlipidemia, SOS, thrombosis, osteonecrosis, and fungal infections)(25).
- Evaluate the effect of Eryaspase on the concurrent maintenance therapy with 6-mercaptopurine and methotrexate. Levels of cytotoxic methotrexate (MTX polyglutamates) and 6-mercaptopurine metabolites (6-thioguanine nucleotides, 6TGN, and methylated metabolites, MeMP) and of DNA-TGN levels in circulating leukocytes.

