8.3.2 Maintenance Metabolites

Maintenance metabolites will be measured once a month during first year of maintenance. Blood samples will be collected at local institutions and sent to: The Laboratory for Pediatric Oncology, Bonkolab 5704, The National University Hospital, Rigshospitalet, Copenhagen, Denmark. Here it will be stored and analysed.

Hematological parametres (Hemoglobin, thrombocytes, White Blood Cell Count) and liver parameters (bilirubin, alanine aminotransferase (ALAT), Lactate dehydrogenase (LDH)) have to be measured at the same time points. Furthermore, details about maintenance therapy have to be filled in the CRF.

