10.2 AEs/SAEs not to be reported

When treating children with cancer, the strategy is generally to treat to the limit of toxicity. Thus, all patients will be at a significant risk of experiencing AE's and SAEs, and all patients and families are informed hereof, when they enter therapy. Most patients will experience febrile neutropenia with or without confirmed bacteraemia, and these are potentially life threatening or may require inpatient hospitalization or prolongation of existing hospitalization. Thus, these AE's and several other SAEs reflect the overall treatment intensity of the current protocols for childhood ALL and not only the

treatment of asparaginase. In addition, treating to neutropenia is in principle the goal of several of the treatment phases and will frequently lead to infections (febrile neutropenia and other infections).

A number of toxicities are so well-known and frequent during therapy that they will not be reported. These includes:

- Since leukopenia is the target toxicity (monitoring parameter), this side-effect will not be regarded as a SAE. This also includes febrile neutropenia leading to hospitalization or prolongation of ongoing hospitalization if the patient's condition otherwise is good with no signs of septic shock.
- Since thrombocytopenia is the target toxicity (monitoring parameter) this side-effect will not be regarded as a SAE.
- A rise in aminotransferases with normal liver function tests (i.e. bilirubin and INR (or coagulation factor 2-7-10) is a well-known side effect of HD-MTX, 6MP and asparaginase and will not be regarded as a SAE.
- A rise in bilirubin to less than 5x UNL.
- Hyperglycemia will not be reported.
- Infection/fever leading to hospitalisation or prolongation of existing hospitalisation.

The overall safety and tolerability of eryaspase in combination with multi-agent NOPHO ALL 2008 or ALLTogether pilot protocol chemotherapy will be evaluated according to the PdL toxicity consensus definitions for asparaginase related toxicities (hypersensitivity, pancreatitis, hyperlipidemia, SOS, thrombosis, osteonecrosis, and fungal infections)(1). Table 3 contains the toxicities potentially related to treatment with asparaginase. All of these toxicities must be reported to PI's and on the CRF.

TABLE 3. POTENTIAL RELATED TOXICITY TO ASPARAGINASE (1)

Toxicity	Consensus definition

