2.4. Secondary Endpoints

2.4.1. Pharmacokinetic Evaluation:

2.4.1.1. Key Secondary Endpoint:

- The percentage of patients with ASNase activity >100 U/L at 14 days following the *fourth* infusion of the 2-week dosing intervals.

Sponsor:	NOPHO – Nordic Society of Pediatric Hematology & Oncology		
Protocol:	NOR-GRASPALL 2016		
Document Version No.:	2.0	Document Date:	14-May-2021

2.4.2. Pharmacodynamic Evaluation:

- Cerebrospinal fluid (CSF) concentrations of asparagine (ASN), aspartate (ASP), glutamine (GLN), and glutamate (GLU)

2.4.3. Immunogenicity:

- Anti-asparaginase antibodies.

2.4.4. Safety and Tolerability:

- Incidence of hypersensitivity (allergic reactions and silent inactivation);
- Adverse events from start of treatment until 30 days after last administration;
- Levels of cytotoxic methotrexate (MTX polyglutamates) and 6 mercaptopurine metabolites (6 thioguanine nucleotides (6TGN) and methylated metabolites (MeMP)) and of DNA-TGN levels in circulating leukocytes.

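### The planned summary of maintenance metabolites ignores the 6MP and MTX dose, so it could understate an eryaspase interaction if doses are cut; add dose-normalised levels beside the raw ones

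*SAP*

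**What the plan says.** Protocol 3.2 makes it a secondary objective to "Evaluate the effect of Eryaspase on the concurrent maintenance therapy with 6-mercaptopurine and methotrexate". SAP 2.4.4 carries this as a secondary endpoint under safety and tolerability: "Levels of cytotoxic methotrexate (MTX polyglutamates) and 6 mercaptopurine metabolites", together with DNA-TGN. The analysis is one sentence in SAP 6.3.2, ending "of DNATGN levels in circulating leukocytes will be summarized over time using descriptive statistics".

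Protocol 1.0 gives the reason for the objective. An analysis of NOPHO data "indicates increments of 6MP and MTX metabolites levels during the treatment of PEG-asparaginase", and PEG-asparaginase "has been previously associated with increased myelotoxicity and higher frequency of 6MP/MTX dose reductions during maintenance therapy for childhood ALL". The same section links higher 6MP metabolite levels to hepatic sinusoidal obstruction syndrome (SOS) and calls for study of other asparaginase formulations.

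Protocol 8.3.2 schedules metabolites monthly in the first year of maintenance, with blood counts and liver tests at the same times. It adds that "details about maintenance therapy have to be filled in the CRF". Footnote r to the Protocol 8.1 schedule also asks for maintenance therapy to be registered in the CRF.

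**The concern.** A metabolite level reflects two things: how much metabolite a patient forms per unit of drug, and how much drug is prescribed and taken. An interaction with eryaspase would act on the first. Clinicians can change the second, and Protocol 1.0 itself reports more frequent 6MP/MTX dose reductions with PEG-asparaginase. If a rise in yield is followed by a lower dose, the raw level moves back towards where it began.

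At stake is how one secondary objective is read. A flat table of raw levels could be taken to show that eryaspase leaves maintenance therapy unaffected, when the effect had appeared as lower doses. Because no planned summary shows dose, a reader of the tables could not tell the two situations apart.

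**Working it through.** **No figure to reproduce.** The documents give no sample size, effect size, standard deviation or power for the metabolite endpoint, so the check has two parts: a search for any use of dose, and the algebra of the scale.

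**Where the SAP could have used 6MP or MTX dose**

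| SAP section | What is planned | 6MP/MTX dose used? |
|---|---|---|
| 4.7 | No covariate-adjusted analysis | No |
| 5.2.4 and 8.4 | Concomitant drugs tabulated by class and term, plus listings | Not in any summary |
| 6.2.3 | Linear dose adjustment of asparaginase activity, 150 to 100 U/kg | No, asparaginase only |
| 6.3.2 | Metabolite levels over time, descriptive | No |
| 7.1 and 7.3 | Dose intensity for asparaginase; compliance with eryaspase infusions | No |
| 8.2 | Laboratory values, changes from baseline and shifts | No |

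Section 6.2.3 shows that the SAP already uses a dose-adjusted scale for another analyte.

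**Algebra.** Let f be the true ratio of level per unit dose with eryaspase to that without it, and c the fractional cut in 6MP or MTX dose. Assume level is proportional to dose. Then:

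- raw ratio = f × (1 − c)
- ratio per unit dose = f × (1 − c) / (1 − c) = f
- cut that makes the raw ratio exactly 1: c = 1 − 1/f

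Neither f nor c is in the documents, so the values below are assumptions shown as a range.

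| Assumed f | Cut that gives a raw ratio of 1.0 |
|---|---|
| 1.2 | 1 − 1/1.2 = 17% |
| 1.3 | 1 − 1/1.3 = 23% |
| 1.5 | 1 − 1/1.5 = 33% |
| 2.0 | 1 − 1/2.0 = 50% |

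For f = 1.5 with smaller and larger cuts:

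- 10% cut: 1.5 × 0.90 = 1.35
- 30% cut: 1.5 × 0.70 = 1.05
- 40% cut: 1.5 × 0.60 = 0.90
- 50% cut: 1.5 × 0.50 = 0.75

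In all four cases the ratio per unit dose stays at 1.5. The cancelling cuts follow from the formula by construction. They show that the raw scale can lose or reverse the signal, not that it will.

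**Is there a contrast to estimate?** SAP 6.3.2 defines none, and the trial has one arm. Under Protocol 7.4.2, eryaspase in NOPHO ALL 2008 patients may start during consolidation, delayed intensification or maintenance, so some monthly samples can fall during eryaspase and others after it. For ALLTogether patients the section describes a start in induction or consolidation, so overlap with maintenance is not established. Dose-normalising alone would therefore not answer the objective; a during/after split is also needed.

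**The case against.** The case against has real weight.

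- **Raw levels fit the endpoint as defined.** Both documents define it as levels, the SAP classes it as safety, and Protocol 12.3 makes all endpoints descriptive. The level actually reached is the quantity that Protocol 1.0 ties to SOS. This stands, and is why the raw summary should be kept. It does not settle the objective, which asks about an effect on maintenance therapy.
- **The earlier NOPHO signal is described as a rise in levels.** So raw levels may show an interaction despite any dose changes. This also stands: masking is possible, not certain. A rise might also show before a cut follows.
- **Other outputs give some cover.** SAP 4.11 promises listings of all CRF data, SAP 8.1 groups events such as leukopenia and veno-occlusive liver disease, and the table shells are in a separate document. Listings do not summarise, however. The adverse-event route is also limited for leukopenia, because Protocol 10.2 says "Since leukopenia is the target toxicity (monitoring parameter), this side-effect will not be regarded as a SAE". That no dose table is planned can be said only of the SAP text.

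A reader might infer three stronger things, and the documents support none of them. First, that 6MP/MTX doses are known to be cut for toxicity in this trial: no rule or rate is given, the cited reductions come from earlier PEG-asparaginase work, and Protocol 10.2 is a reporting exclusion, not a titration rule. Second, that the CRF holds a dose for every metabolite sample: Protocol 8.3.2 ties the blood counts and liver tests to the sampling times, but asks only for details of maintenance therapy. Third, that detecting this interaction is what the trial is for: its primary objective is the pharmacological profile of eryaspase.

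**Conclusion.** The point holds as a worthwhile, inexpensive improvement. For the Protocol 3.2 objective on maintenance therapy, the SAP text offers only raw levels over time and uses no 6MP or MTX dose. If doses are reduced in this trial, as Protocol 1.0 reports with PEG-asparaginase, raw levels could understate an interaction.

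The size is unknown. The illustration of 17% to 50% cuts cancelling rises of 1.2 to 2.0 fold rests on assumed values, strict proportionality, the same cut in every patient and no lag. It should not be quoted as an expected bias. The primary and key secondary analyses are untouched, and the raw levels are not invalid.

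**What to change.** **First confirm** that the CRF details of maintenance therapy include the 6MP and MTX dose, with dates that can be matched to the metabolite samples. The SAP version 2.0 history dropped other analyses because data were not available, so this should not be taken for granted.

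**Then keep the raw summary in SAP 6.3.2 and add:**

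1. Each metabolite per unit of prescribed dose, on the log scale: 6TGN, MeMP and DNA-TGN per mg/m2 of 6MP, and MTX polyglutamates per mg/m2 of MTX. The ratio is undefined when the dose is zero, so samples taken during an interruption should be counted and shown separately.
2. The 6MP and MTX dose at each sample and the percentage of patients with a reduction or interruption, beside the paired white cell count, ALAT and bilirubin.
3. Items 1 and 2 and the raw levels, split by samples taken during the eryaspase period and after it, for patients whose eryaspase overlaps maintenance. The SAP should state where the period ends; the exposure-period definition in SAP 4.2 is one available convention.

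**Cost.** SAP wording, some derived variables and a few tables. No new samples or visits, and no change to treatment. If dose was not recorded, items 1 and 2 are not possible as written, and the report should state that limit.

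**Caveats to print with the tables.** Prescribed dose is an imperfect measure of dose taken. DNA-TGN responds slowly, so its ratio to current dose lags. The during/after split is confounded with time in maintenance and has no control group, so it stays descriptive. None of this implies any rule for 6MP or MTX dosing.
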